Appendix D: Modified International Working Group AML Response Criteria

Hematologic Response According to IWG Criteria for AML	
Category	Definition
Morphologic Complete Remission (CR)	
The following conditions should be met:
 
 • Absolute neutrophil count (ANC) \geq 1000/μL and platelets \geq100,000/μL without transfusions and/or exogenous growth factor support (ie, no transfusion or exogenous growth factor within 7 days of assessment). • Bone marrow with < 5% blasts and evidence of trilineage hematopoiesis. • No evidence of extramedullary disease.
Morphologic Complete Remission With Incomplete Blood Count Recovery (CRi)	
 • ANC < 1000/μL. • Platelets < 100,000/μL or > 100,000/μL without platelet recovery (requiring transfusion within 7 days of assessment). • Bone marrow with < 5% blasts and evidence of trilineage hematopoiesis. • No evidence of extramedullary disease.
Partial Remission (PR)^a	
 • ANC \geq 1000/μL and platelets \geq 100,000/μL without transfusions and/or exogenous growth factor support (ie, no transfusion or exogenous growth factor within 7 days of assessment). • Bone marrow with 5% to 25% blasts and at least a 50% decrease in bone marrow blast percent from baseline. • No evidence of extramedullary disease.

Hematologic Response According to IWG Criteria for AML	
Category	Definition
Treatment Failure	
Resistant Disease: Patient survives ≥ 7 days post-therapy and failed to achieve CR, CRi, or PR with persistent AML in blood or bone marrow.
 
Aplasia: Patient survives ≥ 7 days post-therapy; death while cytopenic, with aplastic bone marrow.
 
Indeterminate cause:
 
 • Patients who die < 7 days post-therapy. • Patients who die > 7 days post-therapy with no peripheral blood blasts, but no bone marrow examination. • Patients who do not complete the first course of therapy. 
Morphologic relapse after CR or CRi:
 
 • the reappearance of $> 5\%$ blasts in the peripheral blood, or • a single finding of $> 15\%$ blasts in the bone marrow. 
All of the above occurrences should be attributed to relapse following CR or CRi and not attributable to another cause (eg, bone marrow regeneration after consolidation therapy).
 
Molecular or cytogenetic relapse: Reappearance of molecular or cytogenetic abnormality.

^a If the pretreatment bone marrow blast percentage was 50% to 100%, the percentage of blasts must decrease to a value between 5% and 25%; if the pretreatment blast percentage was 20% to less than 49%, they must decrease by at least half to a value of more than 5%.

Source: Cheson, 2003.

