9. CONCOMITANT MEDICATIONS AND PROCEDURES

9.1. Permitted Concomitant Medications and Procedures

All supportive care is permitted, including but not limited to:

- Platelet transfusions
- Intravenous immunoglobulin
- RBC transfusions
- G-CSF per American Society of Clinical Oncology (ASCO) guidelines
- Leukapheresis
- Exchange transfusions
- Hemodialysis
- Hydration
- Allopurinol
- Sodium bicarbonate (NaHCO₃)
- Dexamethasone ophthalmic solution or isotears
- Pyridoxine
- Antiemetics
- Chlorhexidine solution
- Pain medications
- Antibiotics
- Anti-herpetics
- Anti-fungals
- Hydroxyurea is permitted prior to start of lenalidomide (Cycle 1 Day 1) and through Day 14 of Cycle 1 if needed to control leukocytosis. Administration will be at the discretion of the investigator.

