10.6. Efficacy Analysis

10.6.1. Primary endpoint

Morphologic complete response rate (CR or CRi) rate within 4 investigational product cycles

The primary endpoint is the morphological complete response rate within a maximum of 4 cycles of treatment. Morphological complete response is defined as CR or CRi. These response criteria will be assessed according to the revised AML IWG Criteria (Cheson, 2003).

The morphological complete response rate is defined as the total number of subjects with morphological complete response observed within the first 4 cycles of study therapy (regardless of whether the CR/CRi is observed at the end of Cycle 1, 2, 3 or 4) over the total number of subjects evaluable for this endpoint (maximum likelihood estimator). The CR/CRi does not need to be present at the end of Cycle 4 if observed before this time for the subject to be considered as having achieved a complete response with regards to the primary endpoint. The corresponding Clopper Pearson 95% confidence interval will be calculated for the response rate. The primary analysis of this endpoint will be based upon the ITT population and the Response Rate population. Decision making with regard to continuation to Stage 2 and at the end of Stage 2 will be based on responses within the Response Rate population.

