10.1. Analysis of Primary Efficacy Endpoint

The primary endpoint is the morphological complete response rate within a maximum of 4 cycles of treatment. Morphological complete response is defined as CR or CRi as assessed locally and reported in the "Modified IWG Response Assessment" eCRF page. These response criteria will be assessed according to the revised AML IWG Criteria (Cheson, 2003, see Section 18.1).

The morphological complete response rate is defined as the total number of subjects with morphological complete response observed within the first 4 cycles of study therapy (regardless of whether the CR/CRi is observed at the end of Cycle 1, 2, 3 or 4) over the total number of subjects evaluable for this endpoint. The CR/CRi does not need to be present at the end of Cycle 4 if observed before this time for the subject to be considered as having achieved a complete response with regards to the primary endpoint. Responses occurring after a treatment failure assessment outcome will not be considered. The corresponding Clopper Pearson 95% confidence interval will be calculated for the response rate.

The primary analysis of this endpoint will be based upon the ITT population and the RR population.

Data as collected in the "Modified IWG Response Assessment" eCRF page will be listed.

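### A cleared marrow with counts recovered after recent G-CSF fits neither CR nor CRi in Appendix D, so a response can drop out of the primary endpoint or be scored differently between sites

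*Protocol*

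**What the plan says.** Protocol Appendix D, repeated in SAP 18.1 Table 4, sets the response categories. CR and CRi share one marrow condition, "Bone marrow with < 5% blasts and evidence of trilineage hematopoiesis", and both require no extramedullary disease. They differ on blood counts and support.

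- **CR:** ANC at least 1000/µL and platelets at least 100,000/µL, "without transfusions and/or exogenous growth factor support (ie, no transfusion or exogenous growth factor within 7 days of assessment".
- **CRi:** ANC below 1000/µL; platelets below 100,000/µL, or above it "without platelet recovery (requiring transfusion within 7 days of assessment". The row does not say whether the ANC and platelet bullets are joined by and or by or.
- **PR:** 5% to 25% marrow blasts.
- **Resistant Disease:** the patient "failed to achieve CR, CRi, or PR with persistent AML in blood or bone marrow".

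Protocol 9.1 permits "G-CSF per American Society of Clinical Oncology (ASCO) guidelines" and "RBC transfusions".

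Only CR and CRi count for the primary endpoint. Protocol 10.6.1 counts a response "regardless of whether the CR/CRi is observed at the end of Cycle 1, 2, 3 or 4", so one qualifying assessment is enough. SAP 10.1 takes the category from the site: "Morphological complete response is defined as CR or CRi as assessed locally and reported in the" IWG response page of the eCRF. SAP 10.1 also disregards any response that follows a treatment failure outcome.

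**The concern.** CR and CRi should together cover every child whose marrow has cleared with trilineage recovery. As written they do not. A child who fails CR solely because of recent growth factor has no CRi bullet to fall into. The ordering is then odd: a child with the same marrow who is still neutropenic and thrombocytopenic is a responder, while one whose counts have recovered after G-CSF has no response category.

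CR/CRi is the numerator of both decisions, at least 3 of 18 to enter Stage 2 and at least 8 of 43 to declare activity. With cut-offs this small, the handling of one or two children can matter. Response is assigned locally at about 70 planned sites, and central review is described only for screening material. Nothing in the plan would bring differing site readings into line.

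**Working it through.** **Step 1: classify the child.** Take a marrow below 5% blasts with trilineage hematopoiesis, no extramedullary disease, ANC at least 1000 and platelets at least 100,000. Vary the support received in the previous 7 days.

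| Support within 7 days | CR? | CRi, bullets joined by or | CRi, bullets joined by and |
|---|---|---|---|
| None | Yes | not needed | not needed |
| G-CSF only | No (growth factor) | No | No |
| RBC transfusion only | No on the literal text; yes if transfusion means platelets | No | No |
| Platelet transfusion only | No | Yes | No |

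The G-CSF row is a gap on every reading. The RBC row is a gap on the literal text. It closes if the CR clause means platelet transfusion, or, with the bullets joined by or, if the CRi clause means any transfusion. The platelet row is a gap only if the CRi bullets are joined by and. PR needs at least 5% blasts and Resistant Disease needs persistent AML, so neither category takes these children. No other section assigns them.

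**Step 2: what happens at that visit.** SAP 10.2.3 lists CR, CRi, PR, Treatment Failure, and missing or not done. A site can enter CRi despite the text, record Treatment Failure, or leave the category blank. The first keeps the response. The second removes it and, under SAP 10.1, any later one. The third loses only that visit.

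**Step 3: reproduce the design.** Inputs from Protocol 10.3: n1 = 18, n2 = 25, continue if X1 ≥ 3, success if X1 + X2 ≥ 8, rates 10% and 25%.

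P(success | p) = Σ over x = 3 to 18 of Bin(x; 18, p) × P(Bin(25, p) ≥ 8 − x)

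- p = 0.25: 0.8003, the planned 80% power
- p = 0.10: 0.0480, within the 5% level
- Stage 1 stop at p = 0.25: P(Bin(18, 0.25) ≤ 2) = 0.1353

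The plan's figures are correct.

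**Step 4: sensitivity.** Let m be the share of true responders never counted at any assessment. The documents give no value, so m is assumed. The rate becomes 0.25 × (1 − m). Expected responders lost are 43 × 0.25 × m, out of 43 × 0.25 = 10.75.

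| m (assumed) | Rate counted | Power | Stage 1 stop at 25% | Responders lost of 10.75 |
|---|---|---|---|---|
| 0 | 0.2500 | 80.0% | 13.5% | 0 |
| 1% | 0.2475 | 79.1% | 14.0% | 0.11 |
| 2% | 0.2450 | 78.2% | 14.6% | 0.22 |
| 5% | 0.2375 | 75.3% | 16.3% | 0.54 |
| 10% | 0.2250 | 69.7% | 19.5% | 1.08 |
| 20% | 0.2000 | 56.4% | 27.1% | 2.15 |

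The error runs one way: at a true 10% rate, the chance of declaring activity falls from 4.8% to 2.8% at m = 10%.

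**The case against.** A reader might infer that every such child is lost from the endpoint and that power is therefore below 80%. The documents do not support either step.

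- **Loss is not automatic.** One qualifying assessment in Cycles 1 to 4 suffices. The child is lost only if every otherwise qualifying assessment falls in the gap, or if a Treatment Failure entry bars what follows. On the same literal reading the child is not a treatment failure, so a careful site would not make that entry.
- **The category is local.** No programmed derivation from counts and support is described. An investigator may reasonably enter CRi for a supported count. The better-documented risk is inconsistency between sites.
- **The power figures are conditional.** The share is assumed, and at 1 to 2% the effect is small. The calculation also takes the planned 25% as the rate before any loss. If 25% was meant under Appendix D exactly as written, power remains 80.0%.
- **The red-cell case is weaker.** The support clause sits in the bullet on ANC and platelets, and the CRi clause concerns platelets. Read in context, transfusion may mean platelet transfusion, which would make the child CR.
- **G-CSF is not at a site's free choice.** Protocol 9.1 ties it to ASCO guidelines.

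All five points stand as limits on frequency and size. None supplies a category for the G-CSF case.

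**Conclusion.** The gap is real and should be fixed. For a cleared trilineage marrow without extramedullary disease, with recovered ANC and untransfused recovered platelets, G-CSF within 7 days leaves the child outside CR, CRi, PR and Resistant Disease on any reading of the rows. After an RBC transfusion the same follows from the literal wording only. The consequence is that a response can be missed at that assessment or scored differently between sites.

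The cost in power ranges from under 1 percentage point at an assumed 1% share to about 24 points at 20% (80.0 − 56.4 = 23.6). Nothing in the documents says where in that range the trial would fall. This is a wording defect in the primary endpoint. It does not show that the trial is underpowered.

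A lesser point: SAP Table 4 as extracted prints a strict inequality for ANC and platelets in the CR row where Appendix D includes the threshold. This may come from the PDF conversion, and it matters only for values exactly at 1000 or 100,000.

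**What to change.** In Appendix D and SAP Table 4:

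1. Define CRi as meeting all the CR conditions on marrow and extramedullary disease but not every CR condition on ANC, platelets, transfusion or growth factor. This also settles how the CRi bullets are joined.
2. State which type of transfusion the CR clause refers to.
3. Confirm that the SAP thresholds include the boundary value, as the protocol's do.

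CR and CRi then cover every cleared trilineage marrow without extramedullary disease, and the shortfall modelled above no longer arises from this source. The change is a sentence or two in each document, with no new assessment and no change to supportive care. The share of CRi within CR/CRi may rise slightly, so the two should be reported separately as well as combined.

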1.4.1. Adult High-Risk MDS and AML Trials

Overall, lenalidomide monotherapy was relatively well tolerated at doses up to 50 mg/day given on Days 1 - 21 of a 28-day treatment cycle, in elderly patients with advanced AML (Blum, 2010; Fehniger, 2011). The observed safety profile was similar to that observed with lenalidomide treatment in patients with other hematological malignancies. No optimal dose or regimen could be established or concluded based on the available data.

In a Phase 1 dose-escalation trial in adults with relapsed or refractory leukemia, 31 patients with AML were treated with acceptable tolerability, a maximum tolerated dose (MTD) of 50 mg/day was established and a dose-limiting toxicity (DLT) of fatigue was observed at 75 mg/day. Five of 31 patients (16%) achieved complete remission and 3 patients of the 5 patients with cytogenetic abnormalities achieved cytogenetic CR (none of which was deletion 5q). Response duration ranged from 5.6 to 14 months. Notably, 2 patients who relapsed following allogeneic bone marrow transplantation achieved CR with lenalidomide (Blum, 2010).

A Phase 2 study of high-dose lenalidomide as initial therapy for newly-diagnosed elderly AML patients (age > 60 years) evaluated the response to lenalidomide 50 mg daily for two, 28-day

cycles followed by low-dose maintenance therapy (10 mg daily) for up to 12 cycles (Fehniger, 2011). Of the 33 patients enrolled, the CR/complete remission with incomplete blood count recovery (CRi) rate was 30% (CRi defined as CR with insufficient hematological recovery of platelets or neutrophils) and was 53% for the 19 patients completing at least 2 cycles of high-dose 50 mg lenalidomide. Median time to CR/CRi was 30 days (range 1 to 72 days) and median duration of CR/CRi was 10 months. The response rate and toxicity profile are favorable compared to other low-intensity agents (Fehniger, 2011).

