6.20.1. Bone Marrow Aspirate or Biopsy and Peripheral Blood

To determine morphologic CR/CRi, BMA/biopsy and peripheral blood smear must be collected from all subjects at screening and at the completion of the 21-day treatment period of the predefined treatment Cycles 1, 2, 3 and 4 within 6 days **before dosing for each subsequent cycle** (ie, between Day 22 to Day 27 of that cycle) (Table 2). If morphologic CR/CRi is achieved within the first 2 cycles, BMA/biopsy and peripheral blood smear will not be required at the end of Cycle 3. For all subjects, BMA/biopsy and peripheral blood smear must be performed at the completion of Cycle 4, and at the Treatment Discontinuation Visit or at the time of suspected relapse (whichever occurs first). For subjects who are assessed as having partial response, the BMA/biopsy and peripheral blood smear will be repeated at Cycle 8 unless the subject goes to allogeneic HSCT, and at the Treatment Discontinuation Visit or at the time of suspected treatment failure (whichever occurs first). ***A bone marrow biopsy is required only if a bone marrow aspirate cannot be obtained.*** Subjects demonstrating clinical benefit as per the Investigator at the end of Cycle 4 and beyond may continue to receive lenalidomide on study for up to 12 cycles in the absence of protocol-defined toxicity or transitioning to allogeneic HSCT.

In the case where a study center has an IRB- and Celgene-approved procedural ICF/IAF that allows collection of additional bone marrow samples for potential research purposes, the latest pre-study PB and BM aspirate/biopsy may be used for screening study assessments.

The screening BMA slide (and/or bone marrow biopsy paraffin embedded slide) and peripheral blood smear slide **must** be provided to the central reviewers at [REDACTED]. The central review [REDACTED] will provide standardized analysis and reporting for all subjects. The central reviewer's assessment will be used retrospectively to confirm diagnosis.

In addition, BMA/biopsy will be obtained to confirm CR, CRi, partial remission (PR), or treatment failure, as assessed by the Investigator based on complete blood count [CBC] with white blood cell (WBC) differential results (defined in Appendix D). Morphological response will be assessed based on peripheral blood count recovery and morphologic assessment of

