6.20.4. Modified IWG Response

Modified International Working Group response (Appendix D) criteria will be used to assess activity at the completion of predefined treatment Cycles 1, 2, 3 and 4 and at the Treatment Discontinuation Visit or at the time of suspected relapse (whichever occurs first). An IWG response assessment will be performed whenever a bone marrow assessment is performed in order to confirm CR or CRi, PR, or treatment failure. For subjects who are assessed as having partial response, the IWG response will be repeated at Cycle 8 unless the subject goes to allogeneic HSCT, and at the Treatment Discontinuation Visit or at the time of suspected treatment failure (whichever occurs first).

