Grade 3 ALT/AST values that return to levels that meet initial eligibility criteria within 7 days of IP interruption do not require a dose reduction. These subjects may resume treatment at the original dose level. If the toxicity recurs, then dose de-escalation is indicated.

Day 1 of Cycle 2 and beyond may be delayed up to 14 days from the end of the prior cycle in order for subjects to recover from toxicity. If a study interruption has lasted for more than 14 days, the Investigator should contact the Medical Monitor to discuss whether the subject should be continued on the study.

Special Instructions for Myelosuppression:

Due to the underlying marrow infiltrating malignancy, myelosuppression is universal and expected in patients with AML. Therefore, myelosuppression (anemia, neutropenia, and thrombocytopenia) will not require dose reduction or interruption *except* in the case of neutropenia or thrombocytopenia due to prolonged bone marrow aplasia at the end of a treatment cycle in subjects who have achieved remission.

- For subjects who have achieved remission:
 - Prolonged bone marrow aplasia is defined as lack of peripheral blood count recovery to $ANC \geq 500/mm^3$ and platelets $\geq 50,000/mL$ without transfusion for 7 days in the absence of leukemia (bone marrow biopsy demonstrate hypocellularity without evidence of leukemia) at Day 43 of a cycle (ie, failure to start the next cycle within 14 days).
 - The lenalidomide dose will be interrupted and the start of the next cycle will be delayed until count recovery.
 - Prolonged delay (ie, failure to start the next cycle within 14 days) for subjects in remission will require dose de-escalation.
 - If the peripheral blood counts recover within 14 days, the subject will proceed to the next cycle without dose reduction.

- If the peripheral blood counts do not recover within 14 days, repeat bone marrow evaluation including bone marrow biopsy every 7-14 days to assess cellularity and to evaluate for relapse/persistent leukemia.
- For subjects who have not achieved remission:
 - In general, subjects who have not achieved remission and have evidence of residual leukemia will proceed to the next cycle as scheduled regardless of count recovery.
- For subjects with residual leukemia:
 - If residual leukemia is demonstrated and the subject previously had achieved CR/CRi, the subject will be discontinued from the study.

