10.3. Sample Size and Power Considerations

Under Simon's Optimal two stage design with a 5% significance level and 80% power, assuming a lower boundary of interest in the response rate of 10% and an upper boundary of interest in the response rate of 25%, a total of 43 evaluable subjects are required for the evaluation of the primary endpoint; 18 in Stage 1 and an additional 25 in Stage 2.

If less than 3 of 18 evaluable subjects in Stage 1 achieve a morphologic response (either CR or CRi) within a maximum of 4 cycles then the study will terminate, otherwise the study shall continue as planned and enrollment of an additional 25 subjects shall continue into Stage 2.

If, at the final analysis, less than 8 of 43 evaluable subjects in both Stage 1 and 2 achieve a response (either CR or CRi) within a maximum of 4 cycles then it will be concluded that lenalidomide, at the dose level tested, does not have sufficient activity in pediatric AML (second

or greater relapse or refractory). However, should at least 8 of the 43 evaluable subjects achieve a response (either CR or CRi) then it will be concluded that lenalidomide, at the dose level tested, demonstrates activity in pediatric subjects with AML (second or greater relapse or refractory) to allow further investigation. Up to 4 additional subjects may be included to account for subjects found to be unevaluable for the primary endpoint (eg, incorrect diagnoses, not having a disease assessment post screening, or who discontinued prior to receiving lenalidomide therapy). The first 43 subjects enrolled and evaluable for the primary endpoint analysis will be used to assess the primary endpoint.

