18. APPENDICES

18.1. Modified International Working Group AML Response Criteria

Hematologic Response According to IWG Criteria for AML is reported in table [Table 4](#).

Table 4: Hematologic Response According to IWG Criteria for AML

Category	Definition
Morphologic Complete Remission (CR)	The following conditions should be met: 
 • Absolute neutrophil count (ANC) > 1000/uL and platelets > 100,000/uL without transfusions and/or exogenous growth factor support (ie, no transfusion or exogenous growth factor within 7 days of assessment). • Bone marrow with < 5% blasts and evidence of trilineage hematopoiesis. • No evidence of extramedullary disease.
Morphologic Complete Remission With Incomplete Blood Count Recovery (CRi)	
 • ANC < 1000/uL. • Platelets < 100,000/uL or > 100,000/uL without platelet recovery (requiring transfusion within 7 days of assessment). • Bone marrow with < 5% blasts and evidence of trilineage hematopoiesis. • No evidence of extramedullary disease.
Partial Remission (PR) ^a	
 • ANC > 1000/uL and platelets > 100,000/uL without transfusions and/or exogenous growth factor support (ie, no transfusion or exogenous growth factor within 7 days of assessment). • Bone marrow with 5% to 25% blasts and at least a 50% decrease in bone marrow blast percent from baseline. • No evidence of extramedullary disease.
Treatment Failure	Resistant Disease: Patient survives ≥ 7 days post-therapy and failed to achieve CR, CRi, or PR but are stable with persistent AML in blood or bone marrow.

Category	Definition
	
Aplasia: Patient survives ≥ 7 days post-therapy; death while cytopenic, with aplastic bone marrow.
 
Indeterminate cause:
 
 • Patients who die < 7 days post-therapy. • Patients who die > 7 days post-therapy with no peripheral blood blasts, but no bone marrow examination. • Patients who do not complete the first course of therapy. 
Morphologic relapse after CR or CRi:
 
 • the reappearance of $> 5\%$ blasts in the peripheral blood, or • a single finding of $> 15\%$ blasts in the bone marrow. 
All of the above occurrences should be attributed to relapse following CR or CRi and not attributable to another cause (eg, bone marrow regeneration after consolidation therapy).
 
Molecular or cytogenetic relapse: Reappearance of molecular or cytogenetic abnormality.

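### The CRi definition does not say how its neutrophil and platelet conditions combine, so a cleared marrow with one unrecovered lineage can be scored as a non-response

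*Protocol*

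**What the plan says.** Protocol Appendix D defines CRi in four bullets: ANC below 1000/µL; platelets below 100,000/µL, or above that level "without platelet recovery (requiring transfusion within 7 days of assessment"); marrow blasts below 5% with trilineage hematopoiesis; no extramedullary disease. SAP 18.1 Table 4 repeats them. Its platelet bullet reads "Platelets < 100,000/uL or > 100,000/uL without platelet recovery (requiring transfusion within 7 days of assessment"). The only connective is the word inside that bullet; none links it to the ANC bullet. The introductory line saying that the conditions should be met stands over the CR row only.

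Appendix D is the operative table. Under Protocol 6.20.4 its "criteria will be used to assess activity at the completion of predefined treatment Cycles 1, 2, 3 and 4". SAP 10.1 fixes who decides: "Morphological complete response is defined as CR or CRi as assessed locally and reported in the" response assessment eCRF page. Central review is described for screening material only. In Protocol 6.20.1 the central reviewer's "assessment will be used retrospectively to confirm diagnosis".

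Two other places bear on intent. Protocol 1.4.1, describing an adult study, has "CRi defined as CR with insufficient hematological recovery of platelets or neutrophils". Protocol 8.2.1, on myelosuppression, speaks of "neutropenia or thrombocytopenia due to prolonged bone marrow aplasia at the end of a treatment cycle in subjects who have achieved remission".

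**The concern.** The marrow and extramedullary bullets must both hold for CRi. The PR row, set out the same way and also without an introductory line, only makes sense if every bullet holds. A site that reads the CRi row in the same way will require low ANC and low platelets together. A child with ANC 1500/µL, platelets 60,000/µL, a cleared marrow and no extramedullary disease is then not CRi; a site that accepts either lineage scores the same child as CRi.

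The count drives both decisions. One subject separates 2/18 (stop) from 3/18 (continue), and 7/43 (insufficient activity) from 8/43 (active). That is true of any binary endpoint, so it shows what is at stake and not how likely an error is.

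A second effect follows from SAP 10.1, which disregards responses after a treatment failure. SAP 10.2.3 offers only CR, CRi, PR, treatment failure or missing as outcomes, and SAP 10.2.2 treats less than PR as treatment failure. If a strict-reading site enters failure at Cycle 1 for a one-lineage subject, a full CR at Cycle 2 would no longer count.

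**Working it through.** **1. Classification.** Take marrow blasts below 5% with trilineage hematopoiesis, no extramedullary disease and no growth factor in the last 7 days, and apply Appendix D.

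| Counts | Both lineages required | Either lineage suffices |
|---|---|---|
| ANC < 1000 and platelets < 100,000 | CRi | CRi |
| ANC < 1000 only | no category | CRi |
| Platelets < 100,000 only | no category | CRi |
| ANC recovered, platelets > 100,000 but transfused within 7 days | no category | CRi |
| Both recovered without support | CR | CR |

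The middle three rows are not CR (both counts must recover), not PR (which needs 5% to 25% blasts) and not resistant disease (which needs persistent AML). They stay in the denominator and leave the numerator.

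**2. Two smaller gaps.** An ANC of 1000 or more reached only with growth factor in the last 7 days, with recovered platelets, fails CR on the growth-factor condition and fails CRi on either reading. Protocol 9.1 permits G-CSF. Separately, Appendix D uses ≥ 1000 and ≥ 100,000 for CR and PR, while SAP Table 4 uses >.

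**3. The plan's own design.** Inputs from Protocol 10.3: n1 = 18, continue if at least 3 respond; n = 43, active if at least 8 respond; rates 10% and 25%.

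P(active | p) = Σ from x = 3 to 18 of P(Bin(18, p) = x) × P(Bin(25, p) ≥ 8 − x)

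P(stop at Stage 1 | p) = P(Bin(18, p) ≤ 2)

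- p = 0.10: P(active) = 0.048, P(stop) = 0.734.
- p = 0.25: P(active) = 0.800, P(stop) = 0.135.

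The stated 5% and 80% reproduce, and the sample size is not in question.

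**4. Illustration.** Let f be the share of responders, on the either-lineage reading, who have exactly one unrecovered lineage, and h the fraction of those scored as non-responders. The documents give neither. If the 25% rate counts one-lineage responders, the counted rate is p = 0.25 × (1 − h × f).

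| f | p, h = 1 | Power | P(stop) | p, h = ½ | Power |
|---|---|---|---|---|---|
| 10% | 0.225 | 0.70 | 0.19 | 0.2375 | 0.75 |
| 20% | 0.200 | 0.56 | 0.27 | 0.225 | 0.70 |
| 30% | 0.175 | 0.41 | 0.37 | 0.2125 | 0.63 |

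The loss shrinks if a one-lineage subject later recovers fully and is scored CR. It does not shrink if failure was entered first.

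**The case against.** The strongest reply is that the intent is plain. The category is named for incomplete count recovery, and one unrecovered lineage is incomplete recovery in ordinary language. The conditions-met line is absent from the CRi row. The strict reading leaves a cleared marrow in no category at all, which is itself a reason to reject it. Protocol 1.4.1 and 8.2.1 both use the either-lineage form. All of this stands as evidence of intent. It does not amount to a rule: 1.4.1 describes another study and 8.2.1 governs dosing. The documents also cite a published standard. It is not reproduced beyond these tables, so it cannot be relied on here to settle the point.

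The reply also notes that safeguards exist. Protocol 6.14.1 records ANC and platelets in the CRF, Protocol 15.2 plans edit checks and queries, and the SAP plans listings of marrow assessments (10), response (10.1) and hematology (11.4.1). This is correct and reduces the extra work needed, but a check needs a stated rule to check against.

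The shares in the illustration are invented, and scoring every affected subject strictly is an extreme. One-lineage cases may be few: Protocol 8.2.1 expects myelosuppression in all patients, and marrow is taken on Days 22 to 27, just after 21 dosing days. That is suggestive only.

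A reader might infer that type I error is inflated, because sites could score more loosely than the null rate assumed. The documents do not support this. Protocol 10.3 says only "assuming a lower boundary of interest in the response rate of 10"%, with no CRi definition attached, and nothing suggests that the null was set on the strict reading.

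**Conclusion.** The point holds as a defect in the endpoint definition. Followed as a list, the CRi row drops subjects whom its own title appears to include; no section states the intended rule for this trial, and no central scoring of response is described.

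Its size cannot be determined from the documents. There is no loss if sites score on the reading behind the 10% and 25% rates. If that reading was either-lineage and some sites score strictly, power falls by an amount that depends on the two unknown fractions in the illustration. A reader might infer that subjects have been misclassified; the documents do not show how any site read the row. The growth-factor gap and the > versus ≥ mismatch are tidying points with no shown effect on the locally reported endpoint. The point should be fixed, at modest priority.

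**What to change.** In Appendix D and SAP Table 4, define CRi as the CR marrow and extramedullary criteria with ANC < 1000/µL and/or platelets < 100,000/µL (or transfusion-supported). State which category applies to an ANC reached only with growth factor. Align the SAP's > limits to the protocol's ≥. Send sites a short clarification, and record that the 10% and 25% rates refer to this definition.

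Keep local assessment as the endpoint source. Check entered categories against recorded counts, transfusions and growth factor use through the edit checks, queries and listings already planned. Add one small check at Stage 1, where SAP 14 plans only AE listings. From Cycle 3, scheduled hematology falls on Day 1 only (Protocol 6.14.1), so a count concurrent with the marrow depends on the blood smear and CBC sample in Protocol Table 2. If responses have already been scored, report the count under both readings.

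The cost is wording in two tables, one site communication and a limited amount of checking. The sample size and decision limits stay as they are.
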